Study Title: The impact of price promotions on purchases of confectionery and snacks: a randomised controlled trial in an experimental online supermarket study

Med IDREC Ref: R65010/RE005

Date 02/12/2021 Version 1.0

Summary of study

Participants (n=500) were asked to imagine they were buying snacks for a night in with 4 friends, with a budget of £5-£10. They were asked to select products from:

- Confectionery
- Biscuits and crackers
- Crisps, nuts and snacking fruit
- Cakes and tarts

They were randomised to one of two groups:

1. Promotions removed: No promotions present on any products
2. Promotions included: Promotions applied to a pre-determined percentage of food products (matching frequency/discount depth found on real online supermarket) within the target categories listed above.

Primary Analysis

Linear regression models will compare the total energy (kcal) purchased in the two groups. Any baseline variables (e.g. demographic characteristics) which appear to have been imbalanced between groups will be adjusted in the model. If no baseline characteristics are needed in models, then simpler t-tests will be considered. Non-parametric equivalents will be used should assumptions for parametric tests be violated.

Sensitivity analysis:

The primary analysis will be run including only participants who spent between £5 and £10 on products from the target categories (Confectionery; Biscuits and crackers; Crisps, nuts and snacking fruit; Cakes and tarts) will be included, to explore the impact for participants who had greater likelihood of being exposed to the promotional activity.

Secondary Outcomes

Linear regression models will compare the two groups on:

- a. total sugar (g, kcal, %E)
- b. total salt (g, kcal, %E)
- c. total saturated fat (SFA) (g, kcal, %E)

Secondary Analyses

1. *Including demographics:* Linear regression models will compare purchases in the two groups, stratified by demographic covariates including gender, age group, ethnic group (White vs Non-White), BMI (<30 and $\geq 30\text{kg}/\text{m}^2$) groups, education level (lower vs. higher), and household income (lower vs. higher) [provided we have sufficient numbers within each subgroup ($n \geq 30$)], with the following outcomes:
 - a. total energy (kcal)
 - b. total sugar (g, kcal, %E)
 - c. total salt (g, kcal, %E)
 - d. total SFA (g, kcal, %E)
2. *By food category:* Linear regression models will also compare differences in purchasing for each of the individual target categories (Confectionery; Biscuits and crackers; Crisps, nuts and snacking fruit; Cakes and tarts) separately, in:
 - a. total energy (kcal)
 - b. total sugar (g, kcal, %E)
 - c. total salt (g, kcal, %E)
 - d. total SFA (g, kcal, %E)

Given the number of comparisons, the threshold for a p-value to be considered significant for secondary analyses will be set at 0.003 (Bonferroni adjustment for multiple comparisons).

Descriptive analysis

The exploratory outcome measures (rating scores and open-ended answers from the follow-up questionnaire) will be discussed descriptively.

Descriptives will also include the number and/or proportion of products bought overall, and by food category and demographics, in the two study groups.

Further descriptives will show the number and/or proportion of products bought on promotion in the promotions applied group, by food category, demographics, and depth of promotion.

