4. OBJECTIVES AND OUTCOME MEASURES

	Objectives	Outcome Measures
Primary	To investigate the effect of promotions on the total number of calories selected	Difference in the absolute energy (kcal) of the final basket between the two groups
Secondary	
To investigate the effect of promotions on the nutritional content of the items selected overall, and across the individual target food categories
 
To explore the impact of removing promotions by socioeconomic status
	
Difference in the absolute sugar (g, kcal, %E), salt (g), and saturated fat (g, kcal, %E) of the final basket between the two groups
 
Difference in the absolute energy (kcal), sugar (g, kcal, %E), salt (g), and saturated fat (g, kcal, %E) between the two groups across the individual target food categories
 
Analyses of the primary and secondary outcomes specified above by gender, age group, ethnic group (White vs Non-White), BMI stratified into <30 and $\geq 30 \text{ kg/m}^2$ groups, education level (lower vs. higher), and household income (lower vs. higher)

Exploratory	To investigate the acceptability of the intervention	Rating scores and open-ended answers from the follow-up questionnaire

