6. INTERVENTION

This study uses a bespoke virtual online supermarket shopping (OLS) platform, hosted by The University of Oxford, which emulates a real online supermarket for research purposes relating to food purchasing interventions (www.woodssupermarket.co.uk). The site is populated with approximately 23,000 current supermarket products drawn from foodDB (April 2019), a weekly updated database of food and drinks available for purchase in six UK online supermarkets (24).

Participants will be asked to imagine they are buying snacks for a night in with 4 friends, with a maximum limit of £10. They will be asked to select products from the following categories, which are aligned and named in the way items are presented in the store:

- Confectionery
- Biscuits and crackers
- Crisps, nuts and snacking fruit
- Cakes and tarts

The shopping task is estimated to take participants 10 minutes to complete. Participants will only be asked to complete the shopping task once. Participants will be provided with the following instructions:

“We would like you to do some online grocery shopping on a supermarket website. This is not a real supermarket, and you will not be asked to spend your own money.

We would like you to imagine you are buying snacks for a night in with 4 friends, up to a limit of £10. You should select products from the following categories:

- *Confectionery*
- *Biscuits and crackers*
- *Crisps, nuts and snacking fruit*
- *Cakes and tarts*

We would ask you not to select any additional items from your usual shopping list.

When doing your shopping, try to imagine you are doing your own grocery shopping and choose foods that you and your friends would eat. You should choose the things you normally buy or wouldn't mind eating.

To make sure you get your reward, please make sure you buy at least £5 worth of products within the suggested food categories”

Participants will be randomly allocated to one of the two following groups when shopping online:

1. Promotions removed: No promotions present on any of the products within the target food categories [confectionery; biscuits and crackers; crisps, nuts and snacking fruit; cakes and tarts] offered to participants when searching for products.

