2. Promotions included: Participants in this group will see a version of the website which will reproduce the types and frequency of promotions that can be found in any online supermarket, for example multi-buy offers and temporary price reductions will be applied to a pre-determined percentage of food products within the target categories [confectionery; biscuits and crackers; crisps, nuts and snacking fruit; cakes and tarts]. Promotions will be applied to match the current levels and types of promotions on the website of the largest UK retailer present in a specific week, shortly before the study launch.

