8.5. Blinding

Investigators will be blinded to intervention allocation and will not be able to manipulate any study parameter following the initial study set up, as all study procedures are taking part in the online platform. The outcome assessment is blinded, as it happens automatically in the online platform. The statistician who will analyse the data will be blinded to intervention allocation. Participants will only be aware of the trial arm that they are exposed to and will be unaware of the other trial arm.

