8.6. Baseline Assessments

Following consent and completion of the shopping task, participants will complete a baseline questionnaire on demographic, shopping, and health data (Appendix B).

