8.8. Discontinuation/Withdrawal of Participants from Study

Each participant has the right to withdraw from the study at any time. Participants will not be replaced as we will recruit sufficient sample size to allow for non-completion rate. Withdrawal from the study, based on the pre-defined completion criteria (section 9.2), will result in exclusion of the data for that participant from analysis.

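### The primary kcal model chooses covariates by apparent imbalance and allows an unnamed non-parametric fallback; one fixed, covariate-adjusted comparison of means would be firmer and costs little

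*SAP*

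**What the plan says.** The primary outcome in protocol section 4 is "Difference in the absolute energy (kcal) of the final basket between the two groups". The SAP (Primary Analysis) compares it by linear regression and sets the covariates by this rule: "Any baseline variables (e.g. demographic characteristics) which appear to have been imbalanced between groups will be adjusted in the model". Protocol section 9.2 repeats the rule. Neither document lists covariates or says how imbalance is judged.

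Only the SAP adds two branches. If no covariate is needed, a t-test may be considered. Then: "Non-parametric equivalents will be used should assumptions for parametric tests be violated". No test, assumption check or threshold is named. Because this sentence follows the one on t-tests, it may apply only to the unadjusted branch.

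Three other statements bear on the point. Protocol section 8.5: "The statistician who will analyse the data will be blinded to intervention allocation". Section 8.6: "Following consent and completion of the shopping task, participants will complete a baseline questionnaire". Section 8.8 says that withdrawal, judged by the completion criterion, "will result in exclusion of the data for that participant from analysis".

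**The concern.** Adjustment improves precision when a covariate predicts the outcome. Whether the covariate happens to differ between randomised arms is a different question. A rule based on apparent imbalance can adjust for variables unrelated to kcal and omit strong predictors that are well balanced. Since the word for imbalance is undefined, the primary model cannot be known until the data are tabulated.

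The non-parametric branch raises a second issue. A bootstrap or permutation test of means would still address mean kcal. A rank test would not estimate the stated outcome, and its power can fall well below that of a mean comparison if only some baskets respond. That is possible here, since in the promotions arm "multi-buy offers and temporary price reductions will be applied to a pre-determined percentage of food products within the target categories". With about 225 per arm, a comparison of means does not need normally distributed data, so the switch is not needed.

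**Working it through.** **1. The plan's own figure.** Inputs from protocol section 9.1: difference 4.5%, SD 15, 90% power, 5% alpha (taken as two-sided), 10% attrition, 500 in total. Standardised effect = 4.5/15 = 0.30. Per arm: 2 × (1.960 + 1.282)² / 0.30² = 233.5, so 234, or 468 in total. Inflation gives 468/0.9 = 520, or 468 × 1.1 = 515, against 500 stated. With 500 × 0.9 = 450 completers (225 per arm), the noncentrality is 0.30 × √(225/2) = 3.18 and exact t-test power is 88.8%. The design roughly reproduces, with no slack on power.

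**2. How open the covariate rule is.** For k independent variables, each flagged with probability p, P(at least one flagged) = 1 − (1 − p)^k. Four readings of imbalance were taken: p<0.05, p<0.10, standardised difference (SMD) above 0.1, and SMD above 0.2. An SMD of 0.1 or 0.2 corresponds to t = 0.1 or 0.2 × √(225/2) = 1.06 or 2.12, so p = 0.289 or 0.034. The pool is also an assumption: four (the questionnaire's demographic block), six (the SAP's subgroup variables) or nine (those six plus household size, weekly spend and online shopping frequency).

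| Pool | Lowest (SMD > 0.2) | Highest (SMD > 0.1) |
|---|---|---|
| 4 | 13% | 75% |
| 6 | 19% | 87% |
| 9 | 27% | 95% |

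**3. Precision given up.** Simulation: 225 per arm, effect 0.30 SD, 10,000 trials per row, nine independent normal covariates, five of them sharing the stated R² equally. All models were fitted to the same trials. Power, %:

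| R² | Rule: p<0.05 / p<0.10 / SMD>0.1 / SMD>0.2 | Fixed five | Gain, points |
|---|---|---|---|
| 0% | 89.2 / 89.2 / 89.0 / 89.2 | 89.1 | −0.1 to 0.1 |
| 5% | 89.3 / 89.4 / 89.7 / 89.2 | 90.7 | 1.0 to 1.5 |
| 10% | 89.7 / 89.9 / 90.5 / 89.6 | 91.9 | 1.4 to 2.3 |
| 20% | 90.3 / 90.6 / 91.9 / 90.1 | 94.5 | 2.6 to 4.4 |

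The differences are more reliable than the levels: the fixed five at R² 0% should be 88.4% by exact calculation, and at 10% it should be 91.4%. An independent repeat gave gains of 1.6 to 2.3 points at 10% and 3.2 to 5.4 at 20%. With covariates correlated at 0.3, the gains were 1.1 to 2.0 and 1.8 to 4.2. Type I error was 3.4% to 4.9% for the rule, 4.8% to 4.9% for the fixed five, and 4.6% to 4.7% with HC3 standard errors.

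**4. What the fixed set can cost.** If no covariate is prognostic, exact power (noncentral t averaged over the chance group-covariate correlation) falls from 88.8% to 88.4% with 5 df, or to 87.9% with 13 df (the suggested five in full categories). Choosing badly also costs something. A set holding three of the five prognostic variables still gains 0.3 to 1.2 points at R² 10% and 0.9 to 2.7 at 20%. A set holding none of them gives 89.0% and 89.2%, which is 0.6 to 2.7 points below the rule.

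**5. If the fallback is a rank test.** Take the plan's 4.5% and read SD 15 as a 15% coefficient of variation (CV) of lognormal basket kcal. Let promotions raise a share q of baskets by r, with r = (1/0.955 − 1)/q = 0.0471/q. The promotions-arm mean is M = 1 + qr = 1.0471, and CV = √[1.0225 × (1 + q(2r + r²)) − M²]/M. For q = 0.3, r = 0.157 and CV = √(1.1264 − 1.0965)/1.0471 = 16.5%.

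| Baskets changed | Promotions-arm CV | Mann-Whitney power | Welch power | Gap, points |
|---|---|---|---|---|
| 100% | 15.0% | 89.3% | 90.1% | 0.8 |
| 50% | 15.7% | 85.9% | 88.5% | 2.6 |
| 30% | 16.5% | 80.5% | 87.0% | 6.5 |
| 20% | 17.5% | 71.6% | 84.9% | 13.3 |

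With equal means and CVs of 15% v 16% to 17%, Mann-Whitney rejects about 5% to 6% of the time, close to nominal.

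**The case against.** The case for leaving the plan alone has weight. The rule causes no bias or type I inflation when applied mechanically, and blinding limits steering. The precision at stake depends on an R² that the documents do not give. The task is standardised ("imagine you are buying snacks for a night in with 4 friends, up to a limit of £10"), so demographics may explain little. The rank-test harm needs three things together: assumptions judged violated, a rank test chosen, and a minority of baskets responding. All of this stands and limits the severity. It does not define imbalance, name the fallback test or supply a reason to prefer balance over prognosis.

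Three stronger readings are tempting and not supported.

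- A reader might infer that the fallback would often reject when mean kcal is equal. Mann-Whitney rejection rates of 7.3%, 14.7% and 40.5% do arise at CVs of 40% v 45%, 50% and 60%. No document gives such CVs, and the responder model above implies only 15% v 15.0% to 17.5%.
- A reader might infer inflated error from choosing among branches. Taking the smallest p-value among the unadjusted, imbalance-adjusted, fully adjusted and rank tests gives 6.7% to 7.9% (ten covariates assumed). That is an upper bound on the freedom left open, and nothing in the plan suggests it would be used that way.
- A reader might call every imbalance pure chance. Covariates are recorded after the task and non-completers are excluded, so imbalance in the analysed set need not be chance alone. Covariate selection by imbalance is still not a remedy for that.

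**Conclusion.** The concern holds as a minor to moderate one. The primary model is open until data are seen, and it selects covariates on a criterion other than prognostic value. The price is about 0 to 1.5 points of power if covariates explain 5% or less of kcal variance, about 1 to 2.5 at 10% and about 2.5 to 5 at 20%. A rank fallback would not estimate the stated outcome. It would lose about 1 to 6.5 points of power when promotions change 100% to 30% of baskets and about 13 at 20%. It would reject with equal means clearly above 5% only if spreads differ clearly, which the documents do not establish.

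Assumptions: R², the prognostic set, the imbalance threshold, the covariate pool, the lognormal shape, the responder share, the use of a rank test, and SD 15 as the spread of basket kcal (it comes from a cited Australian store trial). The t-test option is harmless, since regression on group alone is the equal-variance t-test.

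**What to change.** In the SAP, before unblinded data are seen:

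- Make the primary analysis one linear regression of basket kcal on group, adjusted regardless of balance for a short named set that the task cannot alter. Age, gender, education, household income and household size would serve, coded with few df.
- Do not extend the set to all nine variables: weekly spend and online shopping frequency are self-reported after exposure to the arm.
- Use HC3 standard errors or a bootstrap confidence interval.
- State a missing-category or mean-imputation rule so that nobody is dropped. Age and gender allow a decline-to-answer option, and losing an assumed 5% of participants would take power from about 88.9% to 87.3% (normal approximation).
- Remove the imbalance rule and the non-parametric switch from the primary analysis. Report the unadjusted difference and any rank test as sensitivity analyses.

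The cost is a few sentences, with a matching protocol edit optional. Exact power falls by 0.4 points (5 df) to 0.9 points (13 df) if no covariate is prognostic, and a badly chosen set can do worse than the current rule, as shown above. The team should confirm that unblinded data have not been seen: the SAP, dated 02/12/2021, describes participants in the past tense, which does not in itself show that they have. Because covariates are collected after the task, compare their missingness by arm. The change does not address the exclusion of non-completers.

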9.2. Analysis of Outcome Measures

Completion of the task will be defined as spending at least £5 on products from the target categories.

Primary Analysis

Linear regression models will compare the total energy (kcal) purchased in the two groups. Any baseline variables (e.g. demographic characteristics) which appear to have been imbalanced between groups will be adjusted in the model.

Secondary Analysis

Linear regression models will compare the (i) total sugar (g, kcal, %E), (ii) total salt (g, kcal, %E) and (iii) total SFA (g, kcal, %E) purchased in the two groups.

Secondary analyses will also compare differences in total energy (kcal), total sugar (g, kcal, %E), total salt (g, kcal, %E) and total SFA (g, kcal, %E) across the individual target categories.

We will also conduct secondary analyses of the primary and secondary outcomes specified above by gender, age group, ethnic group (White vs Non-White), BMI stratified into <30 and ≥ 30 kg/m² groups, education level (lower vs. higher), and household income (lower vs. higher) provided we have sufficient numbers within each subgroup ($n \geq 30$).

Descriptive analysis

The exploratory outcome measures will be discussed descriptively.

A Statistical Analysis Plan will be finalised before conducting the statistical analysis.

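### The £5-£10 sensitivity analysis selects on post-randomisation spend, and its £10 ceiling runs against the exposure rationale given for it

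*SAP*

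**What the plan says.** The SAP, under Sensitivity analysis, states: "The primary analysis will be run including only participants who spent between £5 and £10 on products from the target categories". The purpose it gives is "to explore the impact for participants who had greater likelihood of being exposed to the promotional activity". No other sensitivity analysis is planned.

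The protocol sets a lower bound only. Section 9.2 says "Completion of the task will be defined as spending at least £5 on products from the target categories", and section 8.8 says that withdrawal judged by that criterion "will result in exclusion of the data for that participant from analysis". The SAP does not repeat this rule and does not define the population for its primary analysis.

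The £10 figure comes from the task. Participants are told to "imagine you are buying snacks for a night in with 4 friends, up to a limit of £10" (protocol section 6), and the SAP summary gives the budget as £5-£10. Neither document says whether the platform blocks a larger basket, or whether spend means the price paid or the undiscounted price.

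In one arm only, "multi-buy offers and temporary price reductions will be applied to a pre-determined percentage of food products" (protocol section 6). The primary outcome is the absolute energy of the final basket (protocol section 4).

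**The concern.** Two things do not fit.

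First, the rule and its reason point in different directions. Promotions sit in the target categories, so someone who spends more than £10 there has had at least as much contact with promoted products as someone who spends £7. Exposure can justify a floor. It gives no reason for a ceiling.

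Second, the filter is applied to a variable that the intervention can move. Price cuts and multi-buys make the same items cheaper in one arm, and they may also lead people to buy more. Either way, the participants inside the window in one arm need not be comparable with those inside it in the other. Spend is also nearly a proxy for kcal, so cutting the distribution at £10 cuts the outcome directly.

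At stake is how the result is read. Agreement with the primary analysis would be taken as support from more-exposed participants, and disagreement as evidence that exposure matters. Neither reading would be sound.

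**Working it through.** **Who is removed.** There are two readings of the primary population.

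- The protocol rule applies (at least £5, non-completers excluded). The floor then removes nobody new, and the ceiling removes only those above £10.
- The SAP's primary analysis keeps everyone with a basket. The floor then removes light target-category shoppers, which fits the stated reason. The ceiling still removes the heaviest.

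**The plan's own figure.** The plan gives no number for this analysis, so the benchmark is the design effect of 4.5% (SD 15, protocol section 9.1). Two-sided, n per arm = 2 × (1.960 + 1.282)² × 15² / 4.5² = 234, or 468 in total. Allowing for 10% attrition gives 468 × 1.1 = 515 or 468 / 0.9 = 520, against the stated 500. With 225 per arm (500 less 10%), power is 88.9%. The stated size is close enough for 4.5% to serve as the yardstick, and nothing below depends on it.

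**Size of the distortion.** The documents give neither the spend distribution nor the mean discount, so both are assumed. Let list-price spend be normal (μ, σ) in the no-promotions arm, and let kcal be proportional to list value. The mean inside a window (a, b) is

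μ + σ × [φ(α) − φ(β)] / [Φ(β) − Φ(α)], with α = (a − μ)/σ and β = (b − μ)/σ.

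Differences below are promotions included relative to promotions removed, so the protocol's −4.5% appears as a positive figure.

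*Control arm, μ = 8.5, σ = 2.* α = −1.75 and β = 0.75. The mean is 8.5 + 2 × (0.0863 − 0.3011) / 0.7333 = 7.914. The share above £10 is 1 − Φ(0.75) = 22.7%.

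*Case A: a true +4.5% through extra items at full price.* In the promotions arm μ = 8.8825 and σ = 2.09. The mean is 8.8825 + 2.09 × (0.0710 − 0.3458) / 0.6720 = 8.028. The ratio 8.028 / 7.914 = 1.014, so 4.5% becomes 1.4%. With the £5 floor alone it is 4.1%.

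*Case B: identical baskets, lower price paid.* A paid window of £5-£10 at discount d is a list window of 5/(1 − d) to 10/(1 − d). At d = 5% it is £5.26-£10.53, with mean 8.169 and ratio 1.032. At d = 10% it is £5.56-£11.11, with mean 8.416 and ratio 1.063. The truth is 1.000 in both. The floor alone would give about 0.5% and 1.3%, so the ceiling does most of the damage.

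The same formulas across milder assumptions:

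| Assumed μ, σ (£) | Controls above £10 | True 4.5% becomes | False effect, d = 5% | False effect, d = 10% |
|---|---|---|---|---|
| 8.0, 1.0 | 2.3% | 3.6% | +0.5% | +0.8% |
| 8.0, 1.2 | 4.8% | 3.1% | +1.1% | +1.9% |
| 7.5, 1.5 | 4.8% | 2.7% | +1.7% | +3.4% |
| 8.5, 2.0 | 22.7% | 1.4% | +3.2% | +6.3% |

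*Case C: the saving is spent on more food, so paid spend has the same distribution in both arms.* Each paid amount then buys 1/(1 − d) as much kcal. The window keeps the same paid amounts in each arm, and the ratio inside it equals the true 1/(1 − d). There is no distortion. When paid spend is only nearly equal (a true 4.5% with a 5% discount), simulation gives 4.8% to 5.0%.

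**Would undiscounted prices repair it?** Suppose everyone obeys a £10 limit on price paid (normal 8.5, 2, capped at £10) and a 5% discount is spent on more food. The truth is 1/0.95 − 1 = +5.3%. A list-price window excludes promotions-arm participants who paid more than £9.50, which is 1 − Φ(0.5) = 30.9% of that arm, and no controls. Simulation gives −4.3%, the wrong sign. The paid-price window recovers the truth here.

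**The case against.** The strongest reply is that £5-£10 is simply the task. Anyone above £10 ignored an instruction, and setting those baskets aside is a natural adherence check. That is fair as a reason for the ceiling, but it is not the reason the SAP gives, and an adherence subset still does not show an effect in more-exposed people.

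It can also be said that the SAP writes its own £5 floor, which would be redundant if those below £5 had already gone. This stands. A reader might infer that the analysis does the opposite of its purpose throughout, or that only people above £10 can be dropped. The documents do not support that as a flat statement, because the SAP leaves its primary population open and the floor fits the rationale on one reading.

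On size, the larger figures need more than a fifth of controls to exceed a limit they were told to respect. With 2.3% above it, the distortion is small. Cases A and B are also extremes. Under a fixed budget, Case C is plausible and shows none. If the platform enforces £10, the ceiling drops nobody and, under the protocol's completion rule, the analysis merely repeats the primary one. All of this stands and limits the claim to what the rule can do.

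Finally, the analysis is exploratory and carries no decision rule. That limits the consequence, but it is still the only robustness check that readers will have.

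**Conclusion.** The concern holds in a limited form. The window conditions on post-randomisation spend, and its upper bound is not justified by exposure. As written it can bias the kcal contrast in either direction. Over the assumed distributions (about 2% to 23% of controls above £10), a true 4.5% falls to between 3.6% and 1.4%, and a 5% to 10% discount on unchanged baskets produces between +0.5% and +6.3%. The upper end is as large as the effect the trial is designed to find.

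These figures rest on normal spend, kcal proportional to list value, and spend counted at the price paid, which is the plain reading of the SAP but is not stated there. They are illustrations, not predictions. The true share above £10 and the mean discount are unknown, and the distortion is near zero if paid spend is equally distributed across arms. A reader might infer that the sensitivity result is bound to mislead, or that the primary result is compromised. Neither follows, because the primary test does not use this window unless the trial team chooses to apply it there.

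**What to change.** - Delete the exposure rationale from the Sensitivity analysis paragraph of the SAP.
- State the primary population: whether participants below £5 on target categories are in or out.
- Make the sensitivity analysis all randomised participants with basket data, with no spend window, subject to withdrawal requests.
- If the £5-£10 subset is kept, label it a descriptive task-adherence analysis at prices paid, report the numbers below £5 and above £10 by arm, and do not interpret it as a causal or exposure effect. State whether the platform enforces £10.
- Do not use undiscounted prices for the window. They can exclude promotions-arm participants who kept to the budget by using offers.
- Describe exposure from what is already collected: the post-task question on seeing promotions (protocol Appendix B) and the products bought on promotion (SAP, Descriptive analysis).

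The cost is a few lines of SAP text, one extra run of the primary model, and keeping non-completers' basket data. The primary test does not change.

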9. STATISTICS AND ANALYSIS

9.1. The Number of Participants

There are no previously reported standard deviations of the mean difference from similar trials (e.g. where a one-off shop is done) to guide the estimation of the effect size and standard deviation, and, thus, the calculation of the sample size. However, the study by Brimblecombe *et al.* (25) implemented a complex intervention within real supermarkets in Australia where promotions on high sugar products were removed, including confectionery and sugary drinks. This study found a total reduction of -22% in sales (g/MJ) in confectionery, a difference of -4.5% (SD 15) compared to control; and a reduction of -8% in sugar-sweetened soft drinks, a difference of -13% compared to control.

A total sample of 500 participants (250 in each group) would be needed to detect a minimum effect size of -4.5% in total kcal from the target categories, with 90% power, 5% alpha and 10% attrition.

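### Subgroup effects are tested one stratum at a time at 0.003, with no planned estimate of the difference between strata, although an objective asks about impact by socioeconomic status

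*SAP*

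**What the plan says.** Section 4 of the protocol, and its synopsis, list a secondary objective: "To explore the impact of removing promotions by socioeconomic status". The matching outcome measure is analysis of the primary and secondary outcomes by six demographic variables, of which education and household income are the socioeconomic ones.

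The SAP, Secondary Analyses 1, gives the method: "Linear regression models will compare purchases in the two groups, stratified by demographic covariates including gender, age group", followed by the remaining variables and the energy, sugar, salt and saturated fat outcomes. Protocol section 9.2 says only that outcomes will be analysed by these variables, "provided we have sufficient numbers within each subgroup", with a minimum of 30. For judging results the SAP says "the threshold for a p-value to be considered significant for secondary analyses will be set at 0.003", as a Bonferroni adjustment.

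Neither document mentions an interaction term, a test of heterogeneity, or an estimate of how far the effect differs between strata. The SAP's other output by demographics is descriptive: numbers or proportions of products bought.

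**The concern.** Whether removing promotions works differently in lower and higher socioeconomic groups is a question about the difference between two stratum effects. The plan produces an effect estimate in each stratum and a significance call on each. It plans no estimate of the difference and no statement of its uncertainty.

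The documents do not say that a result significant in one stratum and not in the other will be read as a difference in effect. They leave that reading open, and the separate calls at 0.003 are the only decision output planned for the question. Such split results arise easily by chance when each stratum has low power. The protocol's background ties dietary inequalities to health inequalities and says evidence on removing promotions could inform policy, so an unsupported claim of a differential effect would matter.

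**Working it through.** **Inputs from the documents.** Effect and SD: "a difference of -4.5% (SD 15) compared to control" (protocol 9.1), so 4.5/15 = 0.30 SD. Sample: 500 randomised 1:1 with 10% attrition, so 450 analysed, 225 per arm. Threshold for secondary analyses: 0.003 (SAP). Minimum subgroup size: 30.

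**Assumptions.** Two-sided tests. The same true effect in both strata. Stratum splits of 50:50, 30:70, and one stratum at the minimum size, because the documents give no stratum sizes or cut-points. The minimum of 30 is read as 30 in total (15 per arm) and, alternatively, as 30 per arm.

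**The plan's own figure.** Two-sample power with 225 per arm, 0.30 SD and alpha 0.05 is 88.9% (normal approximation), close to the stated 90%. The planning inputs are therefore read correctly.

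**Step 1: power within each stratum.** This uses the noncentral t with n per arm in the stratum, noncentrality d·√(n/2), and alpha 0.003. At d = 0.30:

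| Split | n per arm | Power, smaller / larger stratum |
|---|---|---|
| 50:50 | 112 / 113 | 0.228 / 0.231 |
| 30:70 | 67 / 158 | 0.104 / 0.375 |
| Minimum 30 in total | 15 / 210 | 0.014 / 0.536 |
| Minimum 30 per arm | 30 / 195 | 0.032 / 0.491 |

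**Step 2: chance that exactly one stratum passes.** The strata are independent, so this is p1(1−p2) + p2(1−p1). For 50:50 it is 0.228 × 0.769 + 0.231 × 0.772 = 0.354. Over a range of true effects:

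| True effect | 50:50 | 30:70 | 15 per arm in small stratum | 30 per arm in small stratum |
|---|---|---|---|---|
| 0.30 SD | 35% | 40% | 53% | 49% |
| 0.20 SD | 13% | 14% | 18% | 17% |
| 0.10 SD | 3% | 3% | 3% | 3% |
| None | 0.6% | 0.6% | 0.6% | 0.6% |

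**Step 3: what an interaction test does in the same trials.** In 400,000 simulated trials per split with a common 0.30 SD effect, the interaction has p<0.003 in 0.3% overall, as it should. Among trials where exactly one stratum passes, it is positive in 0.4% to 0.8%. The split pattern is thus almost never accompanied by a positive interaction.

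**Step 4: precision of the interaction.** SE = 15·√(2/n1 + 2/n2), with n1 and n2 per arm. For 50:50 this is 15·√(2/112 + 2/113) = 2.83 points. The half-widths use the t distribution.

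| Split | SE (points) | 95% CI half-width | Power at 0.003 for a 4.5-point difference |
|---|---|---|---|
| 50:50 | 2.83 | 5.6 | 8% |
| 30:70 | 3.09 | 6.1 | 6% |
| 15 per arm in small stratum | 5.67 | 11.1 | 1.5% |

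**The case against.** The objective is only to explore, and its outcome measure asks for analyses by subgroup. Stratified regressions supply an effect in each group, from which a reader could form a contrast. Nobody has written that discordant significance will be taken as effect modification. All of this is true, and it limits the fault to an unplanned contrast and an open interpretation. It does not remove it: the plan fixes a significance threshold for each stratum and nothing for the comparison between strata.

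The largest percentages are also the least secure. The SD of 15 comes from an intervention in real stores measured on sales, and protocol 9.1 itself says "There are no previously reported standard deviations of the mean difference from similar trials". If the standardised effect is 0.10, the usual result is that neither stratum passes and split results are rare. The column with a stratum at the minimum size is a boundary case, and nothing suggests that the education or income strata will be that small. Both points stand. The 50:50 and 30:70 columns, read across the range of effects, are the fair summary.

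Finally, the interaction is badly underpowered, and 0.003 does not control error over the whole set. With 60 tests, if independent, the chance of at least one false positive is 1 − 0.997^60, about 16%. This is a reason to present the interaction as exploratory and to emphasise the interval. It does not favour separate stratum calls, which conceal the same imprecision. A narrower remedy, limited to energy by education and income, would cover the core of the objective.

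**Conclusion.** The concern holds. The plan contains no estimate or test of the difference in effect between strata, and that omission depends on no assumption. How often it could mislead does. With a common true effect and 450 analysed, exactly one of two strata passes at 0.003 in 35% to 40% of trials at the design effect of 0.30 SD for splits of 50:50 to 30:70, in 13% to 14% at 0.20 SD, and in about 3% at 0.10 SD. The splits are assumed, and the 0.30 SD rests on an SD that the protocol does not draw from a similar trial. The issue is confined to secondary, exploratory questions. It should be corrected in the SAP, and the primary analysis is untouched.

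**What to change.** For each demographic variable, fit one full-sample regression with terms for randomised group, subgroup and their interaction, using a joint test where there are more than two levels. Report the interaction estimate with its 95% CI, labelled exploratory, and hold any interaction p-value to the SAP's 0.003. Show stratum effects with CIs but without separate significance calls. State that a difference between strata will be claimed only from the interaction. Name education and household income as the variables that address the socioeconomic objective.

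The cost is SAP wording and a few model lines, with no new data. The ten outcome measures in the SAP (energy, plus three each for sugar, salt and saturated fat) by six variables give 60 interaction tests, 20 of them for education and income. With salt in grams only, as in the protocol's outcome table, eight measures give 48. The price is imprecision: at a 50:50 split the half-width of 5.6 points exceeds the 4.5-point design effect, so most subgroup results will be reported as inconclusive.
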